9.7.3.3 Statistical Methods for Analysis of Effectiveness Variables

The simple percentage of patients achieving SVR12 will be calculated and an exact two-sided 95% confidence interval (CI) of the percentage will be computed based on the Clopper-Pearson method.

Corresponding methods will be used for other response rates (EoT response rate, relapse rate, viral breakthrough). The relapse rates will be estimated in patients of the CP analysis groups with EoT response and sufficient HCV RNA measurements post-

treatment. Viral breakthrough rates will be estimated in all patients of the CP analysis groups, who have at least one undetectable HCV RNA measurement on-treatment and at least one on-treatment or EoT measurement thereafter.

Univariate and multiple logistic regression (MLR) methods will be used to investigate the impact of the following explanatory covariates on SVR12:

- Key demographic information
- Mode of CHC infection
- HCV RNA level at baseline
- Most recent stage of liver fibrosis
- HCV genotype and subtype (if available)
- Type of treating institute
- Liver and/or CHC related co-morbidities
- Key clinical chemistry and hematology laboratory variables at baseline
- In treatment experienced patients only:
 - Most recent prior treatment for CHC
 - Outcome of most recent prior CHC treatment

Further details and additional covariates will be specified in the SAP.

These analyses will be of exploratory nature, data driven, and will be repeatedly performed for various CP Analysis Groups, since not each covariate might be predictive in each patient group. Furthermore, the fact that treatment regimens will differ in the various patient groups has to be taken into account, when selecting the patient groups for each MLR analysis. Backward selection procedures will be applied to generate the final MLR models which consider only covariates in the selection procedure with a p-value <0.25 in the corresponding univariate logistic regression analysis. A p-value <0.05 will be used for the covariates to stay in the model in a backward elimination step. Logistic regression methods will also be used to investigate the impact of treatment adherence on SVR12.

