#### 7.4 Multicenter studies

The clinical study Protocol doesn't contain information about the number of centers.

Data from all centers will be merged and analyzed as one population for all study endpoints.

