**P15-743 (HCV RWE) \_ STATISTICAL ANALYSIS PLAN \_ Final 2.0 \_ 02 Feb 2018**

---

- relapse (HCV RNA <50 IU/mL at EoT or at the last on-treatment HCV RNA measurement followed by HCV RNA  $\geq$ 50 IU/mL post-treatment);
- premature study drug discontinuation with no on-treatment virologic failure;
- missing SVR12 data;
- the percentage of patients achieving SVR24 (single last HCV RNA <50 IU/mL 24 weeks after the last actual dose of the ABBVIE REGIMEN);
- the percentage of patients with virological response (HCV RNA <50 IU/mL) at EoT.

Due to the fact that in the Russian clinical practice tests for HCV RNA often have limit of detection higher than 50 IU/mL (for example, 60 or 100 IU/mL), additional analysis will be performed. In this case all above mentioned effectiveness endpoints will be analyzed with the following definitions:

- the percentage of patients achieving SVR12 (single last HCV RNA value <50 IU/mL or undetectable/negative 12 weeks after the last actual dose of the ABBVIE REGIMEN);
- the percentage of patients with at least one and each of SVR12 non-response categories:
  - breakthrough (at least one documented HCV RNA value <50 IU/mL or undetectable/negative followed by HCV RNA value  $\geq$ 50 IU/mL or positive during treatment);
  - failure to suppress (each measured on-treatment HCV RNA value  $\geq$ 50 IU/mL or positive);
  - relapse (HCV RNA value <50 IU/mL or undetectable/negative at EoT or at the last on-treatment HCV RNA measurement followed by HCV RNA  $\geq$ 50 IU/mL or positive post-treatment);
  - premature study drug discontinuation with no on-treatment virologic failure;
  - missing SVR12 data and/or none of the above criteria;
- the percentage of patients achieving SVR24 (single last HCV RNA value <50 IU/mL or undetectable/negative 24 weeks after the last actual dose of the ABBVIE REGIMEN);
- the percentage of patients with virological response (HCV RNA value <50 IU/mL or undetectable/negative) at EoT.

Achieving SVR12 and presence of breakthrough, relapse or failure to suppress as well as virological response at EoT will be analyzed using univariate logistic regression for both cases (main and sensitivity analyses). These analyses will be of exploratory nature, data driven, and will be repeatedly performed for various CP analysis groups, since not each covariate might be predictive in each patient group. The following parameters can be included in the univariate models as explanatory variables (fixed effect or covariate):

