### 11.1 Exposure

Tables with descriptive statistics in accordance with section 7.1 will be presented for the following parameters:

- actual duration ABBVIE REGIMEN (in days);
- the number of patients with collected deviating duration reasons;
- adherence ABBVIE REGIMEN (calculated for Paritaprevir/R-Ombitasvir, Dasabuvir and Ribavirin separately):
  - percentage of target dose taken in treatment intervals (weeks 1-4, 5-8 and 9-12) for Paritaprevir/R-Ombitasvir and for Dasabuvir;
  - percentage of patients who missed of study drug administration for at least 7 days in a row (only for Paritaprevir/R-Ombitasvir and Dasabuvir).

All corresponding listings will be presented.

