### **16 Summary of changes to the Protocol**

The analyses methods in this SAP is fully consistent with the clinical study Protocol. The MLR analysis for the PSP results will not be performed due to lack of main predictor variability (the fact of the PSP usage is always “Yes”).

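### SAP section 9 omits the adherence–SVR12 regression and the type-of-institute covariate that the supplied protocol commits to, and section 16 records neither omission

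*Protocol*

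**What the plan says.** **Protocol 9.7.3.3.** Univariate and multiple logistic regression "methods will be used to investigate the impact of the following explanatory covariates on SVR12". One entry in the list that follows is "Type of treating institute". Adherence is not in that list. It has its own sentence at the end of the section: "Logistic regression methods will also be used to investigate the impact of treatment adherence on SVR12". The abstract (section 4.0) mentions both analyses. The role left to the SAP is to elaborate and to add: "Further details and additional covariates will be specified in the SAP".

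**Data collection.** Section 9.2.4 of the protocol says the type of institute is entered in the eCRF. Section 9.4.1.2 and Table 2 collect the percentage of target dose taken at the on-treatment, mid-treatment and end-of-treatment visits. Section 7.2 gives the effect of adherence on outcome as something the study will provide data on.

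**SAP.** Section 9 introduces its list with "The following parameters can be included in the univariate models as explanatory variables". Neither institute type nor adherence is in the list. Section 11.1 summarises adherence descriptively in the safety population, as "percentage of target dose taken in treatment intervals (weeks 1-4, 5-8 and 9-12"), together with actual treatment duration and the share of patients who missed at least 7 days in a row. Section 13 states that there will be no other analyses. Section 16 says "The analyses methods in this SAP is fully consistent with the clinical study Protocol", then reports one departure, the PSP regression, and gives the reason for it.

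**The concern.** The protocol commits to two analyses that the SAP does not specify. If the SAP is followed as written, the effect of adherence on SVR12, which the protocol gives as part of its rationale, gets no answer. Nor does the question whether response differs by type of treating institute.

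Section 16 makes this harder to notice. It shows that the authors knew a dropped regression should be recorded and explained, since they did so for the PSP. A reader who relies on that section would conclude that nothing else was dropped.

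There is a related gap in the descriptive summary. The SAP provides for 12-week and 24-week regimens, but the dose-percentage intervals end at week 12.

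**Working it through.** The check is mainly a comparison of lists. The only figure in the plan that bears on it is the sample size, which sets how many failures any predictor model can draw on.

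**1. Covariate headings in protocol 9.7.3.3 against SAP section 9**

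| Protocol heading | In the SAP list? |
|---|---|
| Key demographics | Yes: age, gender, race |
| Mode of infection | Yes |
| Baseline HCV RNA | Yes |
| Most recent fibrosis stage | Yes: seven measures of liver disease stage |
| Genotype and subtype | Yes |
| Type of treating institute | **No** |
| Liver or CHC related co-morbidities | Yes |
| Baseline chemistry and haematology | Yes: ten items |
| Most recent prior treatment | Yes, as treatment experience |
| Outcome of prior treatment | Yes |

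Nine of ten headings have a counterpart. The separate adherence model has none.

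**2. Size of the SAP list.** Demographics 3, mode of infection and genotype 2, baseline HCV RNA 1, liver disease stage 7, co-morbidities 1, prior treatment 1, prior outcome 1, haematology 3 (prothrombin time/INR counted once), chemistry 7. Total: 3 + 2 + 1 + 7 + 1 + 1 + 1 + 3 + 7 = 26 candidates.

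**3. Whether the analyses appear elsewhere in the SAP.** Adherence appears only in section 11.1 and its exposure table shell (Table 4.1). Institute type appears nowhere. Section 13 closes off other analyses.

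**4. The plan's own figure.** Protocol 9.5 states 158 patients for a two-sided 95% Clopper-Pearson interval no wider than 10 points at SVR12 = 90%. Exact limits from beta quantiles, with x = 0.90 × 158 = 142.2, are 84.23% to 94.20%, a width of 9.97 points. The smallest n with width at most 10 points is 158, so the figure reproduces. Nothing in this point changes it.

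**5. Failures available to a predictor model, at n = 158**

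- SVR12 90%: 158 × 0.10 = 15.8
- SVR12 95%: 158 × 0.05 = 7.9

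Failures per candidate with the 26 already listed: 15.8 / 26 = 0.61 and 7.9 / 26 = 0.30. With institute type added as a 27th: 15.8 / 27 = 0.59 and 7.9 / 27 = 0.29.

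**6. Adherence intervals.** Weeks 1-4, 5-8 and 9-12 cover 12 weeks. For a 24-week regimen the dose percentage is therefore not summarised for 24 − 12 = 12 weeks, half of the scheduled period. Actual duration and the 7-day flag in the same section are not limited to week 12.

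**7. Population.** SAP section 6 removes from the core population patients whose treatment ended on or before day 55 (12-week regimens) or day 139 (24-week regimens). An adherence model in the core population alone would lack some of the lowest-exposure patients. The target population keeps them, and the SAP already plans its regression tables there (2.3.X.X).

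**The case against.** **The protocol version.** The SAP says it was written from Protocol version 4.0 of 11 July 2017, and the protocol supplied is version 3.0 (country version 1.0). If version 4.0 removed these analyses, section 16 could be right. This cannot be checked here. The SAP gives no sign of such a removal and keeps the predictor objective, but the finding must be worded as a difference from the supplied version.

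**Permissive wording.** SAP section 9 says what can be included, and the univariate shell ends in an ellipsis, so the two analyses are not forbidden. That is true, but an option does not fulfil a commitment, and no adherence variable is defined for any model.

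**Small consequence.** The protocol calls these regressions exploratory and data driven, and failures will be few. This stands, and it limits the weight of the point. It does not explain the omission, because the SAP accepts 26 other candidates under the same constraint.

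**Stronger readings the documents do not support.**

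- *The predictor objective gets no analysis.* It does: the 26 candidates go through univariate and backward-selected multiple regression for SVR12.
- *Regimen was wrongly left out as a covariate.* The protocol asks that regimen differences be considered when choosing patient groups for each model. The SAP repeats the regressions with and without ribavirin, which meets part of this, although duration is not covered.
- *FibroScan had to be a candidate.* The protocol asks only for the most recent fibrosis stage, and the SAP offers seven measures.
- *Pooling centres is a contradiction.* The SAP does say "Data from all centers will be merged and analyzed as one population for all study endpoints", but type of institute is not the same as centre, and pooled data can still carry an institute covariate.

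**Conclusion.** The point holds as a gap between the SAP and the supplied protocol. One of ten listed covariate headings and one separately promised model are not specified, and section 16 discloses neither. The adherence model is the more important of the two, because the protocol makes adherence part of its rationale. For 24-week regimens, the dose-percentage summary also omits the second half of treatment. How much that matters is unknown: the documents do not give the number of 24-week patients, and the treatment columns named in the exposure shell are 12-week only.

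The effect is confined to exploratory secondary analyses. The primary SVR12 estimate and the sample size do not change. The conclusion assumes that version 4.0 kept the two commitments and that the variables were collected as the protocol plans.

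**What to change.** 1. Add type of treating institute to the candidate list in SAP section 9.
2. Add a separate logistic regression of SVR12 on adherence. Use the percentage of target dose taken over the treatment period, plus the flag for at least 7 consecutive days missed. State whether the denominator is the scheduled or the actual period, since a patient who stops early can score high on the actual one.
3. Run the adherence model in the target population as well as the core population.
4. Extend the dose intervals in SAP 11.1 and its shell to weeks 13-24 for 24-week regimens.
5. If either analysis is deliberately dropped, or was removed in Protocol version 4.0, say so in SAP 16 and give the reason.

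The cost is SAP wording and a few extra models on data the protocol already collects. The drawback is more exploratory results resting on about 8 to 16 failures, so estimates will be imprecise and should be reported as such.

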9.7.4 Clinical Laboratory Data

All reported clinical laboratory test results will be assigned to one of the time points using the time windows specified in the table below.

Table 4 - Analysis Time Windows

Phase	Time point	Time Window
Pre-Treatment	Baseline	Last value prior to start of study treatment (i.e. \leq study day 1)
Treatment Weeks		Study day during treatment period (Study day 1 = first treatment day)
	4 (day 29)	15 – 42
	8 (day 57)	43 – 70
	12 (day 85)	71 – 98
	16 (day 113)	99 – 126
EoT	Actual EoT	Study day of last dose (28 days prior to EoT - 14 days post EoT)
Post Treatment	4 weeks (day 29 post EoT)	15 – 56 post EoT
	12 weeks (day 85 post EoT)	57 – 112 post EoT
	24 weeks (day 169 post EoT)	141 – 196 post EoT

Mean changes from baseline to each post-baseline visit will be summarized descriptively.

Laboratory data values collected during the treatment period will be categorized as low, normal, or high based on reference ranges used in this study. The number and percent of patients who experience post-baseline shifts during treatment in clinical laboratory values from low/normal to high and high/normal to low based on the reference range will be summarized.

Additional details of the analyses of clinical laboratory data will be specified in the SAP.

9.7.5 Patient Questionnaires

The EQ-5D-5L is a health state utility instrument that evaluates preference for health status (utility). The EQ-5D-5L comprises 5 dimensions (mobility, self-care, usual activities, pain/discomfort, anxiety/depression) each of which are rated on 5 levels of

Confidential Information

No use or disclose outside AbbVie is permitted without prior written authorization from AbbVie

Version 3.0 (22 Apr 2015) – country v 1.0 dated 26.06.2015

Page 37 of 61

severity (1: indicating no problem, 2: indicating slight problems, 3: indicating moderate problems, 4: indicating severe problems, 5: indicating extreme problems), and a separate VAS.

Patients' responses to the EQ-5D-5L will be combined into a unique health state using a 5-digit code with one digit from each of the 5 dimensions representing the level of severity. These EQ-5D-5L states will be converted into a single preference-weighted health utility index score by applying country-specific weights (if available) or US weights (if not available).

No imputation will be performed for missing items, and in case of missing items no index score will be calculated.

A summary table will show descriptive statistics (n, mean, median, SD, minimum and maximum) of the index score values and for the VAS values for baseline and the post-baseline time points, as well as changes from baseline both for the index score values and for the VAS values. In addition analysis of covariance (ANCOVA) will be applied to investigate the effect of the different ABBVIE REGIMENS (\pm RBV and duration) on EQ-5D-5L endpoints using the corresponding EQ-5D-5L baseline values as covariates.

Assessments of work productivity and activity impairment as assessed by the WPAI Hep C v2.0 will be evaluated according to the WPAI-SHP scoring manual. The WPAI yields four types of scores, the results of which will be presented as percentage of impairment from 0 to 100. Higher percentages indicate greater impairment:

1. % absenteeism: percentage of work time missed due to hepatitis C
2. % presenteeism: percentage of impairment while working due to hepatitis C
3. % TWP: percentage of overall work impairment due to hepatitis C
4. % TAI: percentage of general (non-work) activity impairment due to hepatitis C

The WPAI Hep C v2.0 consists of 6 questions aimed at the following targets:

- Q1. currently employed (yes, no)
- Q2. hours missed due to hepatitis C in the last seven days
- Q3. hours missed due to other reasons in the last seven days
- Q4. hours actually worked in the last seven days
- Q5. degree hepatitis C affected productivity while working
- Q6. degree hepatitis C affected regular activities

The four scores will be derived as follows:

1. % absenteeism: $100 \times Q2 / (Q2 + Q4)$
2. % presenteeism: $100 \times Q5 / 10$

Confidential Information

No use or disclose outside AbbVie is permitted without prior written authorization from AbbVie

Version 3.0 (22 Apr 2015) – country v 1.0 dated 26.06.2015

Page 38 of 61

3. % TWP: $100 * \{Q2/(Q2+Q4) + [Q4/(Q2+Q4)] * Q5/10\}$
4. % TAI: $100 * Q6/10$

A score will be set to missing if one or more of the items Q1-Q6 that are needed for the calculation of the score are missing. No imputation will be performed for missing items.

The summary table will present the absolute and relative frequencies of employed and unemployed patients and descriptive statistics for the four scores. Further details of the analysis will be specified in the SAP.

9.7.6 PSP and PAM

The contribution of the patient support program (PSP) to disease control, treatment continuation over time, patient satisfaction and PSP utilization will be analyzed using descriptive and exploratory statistical methods. Appropriate frequency tables will summarize all corresponding variables of the PSP questionnaire (see ANNEX 4 and 5) over time stratified by ABBVIE REGIMEN arms. In addition, multiple logistic regression (MLR) analysis will be performed to investigate the association between the use of the PSP and the patient satisfaction variables of the PSP questionnaire with the probability of treatment completion. These MLRs will be performed similar to the MLRs for SVR12 (see Section 9.7.3.3. Additional details will be specified in the SAP).

The Patient Activation Measure (PAM) 13 item scale is a measure used to assess the patient knowledge, skill, and confidence for self-management. Each of the 13 items can be answered with one of four possible response options, which are “disagree strongly” (1), “disagree” (2), “agree” (3), “agree strongly” (4).

Based on responses to the 13-item measure, the score is calculated by adding up the raw scores (range of the sum: 13 – 52) and mapping up the value onto a scale of 0–100 indicating strength of agreement with the 13 items $(100 * (\text{sum} - 13) / (52 - 13))$. The final score can be assigned to one of the four levels of activation. A higher score indicates that the patient is likely to participate more actively in health care processes and takes more responsibility for his or her health.

In case of missing item values, the mean value of the available items will be used for replacement. However, if there are less than nine items answered, no summary score will be calculated.

A summary table will show descriptive statistics (n, mean, median, SD, minimum and maximum) for the summary score at baseline and the post-baseline time points, as well as changes from baseline. In addition analysis of covariance (ANCOVA) will be applied to investigate the effect of the different ABBVIE REGIMENS (\pm RBV and duration) on the

Confidential Information

No use or disclose outside AbbVie is permitted without prior written authorization from AbbVie
Version 3.0 (22 Apr 2015) – country v 1.0 dated 26.06.2015 Page 39 of 61

summary score using the corresponding baseline value as covariates. Further details will be specified in the SAP.

9.7.7 Tolerability Analysis

All tolerability variables will be summarized using descriptive statistical methods for the SP stratified by type of combination treatment and scheduled treatment duration.

All SAEs, non-serious AEs and pregnancy occurrences are to be reported for patients included in the study (see Section 11.0 and 9.2.3). AEs will be coded using MedDRA. The number and percentage of patients with treatment-emergent AEs (i.e. any reported event that begins or worsens in severity after initiation of study drug through 30 days post-study drug dosing) will be tabulated by primary MedDRA SOC and PT. Corresponding summary tables will be provided for all serious treatment-emergent AEs. The tabulation of the number of patients with treatment-emergent AEs by severity and relationship to study drug will also be provided. Patients reporting more than one AE for a given MedDRA PT will be counted only once for that term using the most severe incident for the severity summary table and the most related for the relationship summary table. Patients reporting more than one type of event within a SOC will be counted only once for that SOC.

Additional details of the analysis of AEs will be specified in the SAP.

9.7.8 Interim Assessments

Not applicable for this study.

9.8 Quality Control

The sites will be instructed in the protocol, the functionality and handling of the eCRF, and the requirement to maintain source documents for each patient in the study (see Section 9.4).

A comprehensive data validation program utilizing front-end checks in the eCRF will validate the data. Automated checks for data consistency will be implemented, discrepancies need to be solved by the researcher in the eCRF before the module can be completed. Follow-up on eCRF data for medical plausibility will be done by AbbVie personnel (or their representatives). The principal investigator of each site will finally

review the eCRFs for completeness and accuracy of available data and provide his or her electronic signature and date to eCRFs as evidence thereof.

Continuous monitoring of the study and frequent site telephone contacts will be done by AbbVie or a CRO working on behalf of AbbVie.

